generates model basis set of MRS signals for the following 17 metabolites: alanine, aspartate, creatine (Cr), phosphocreatine (PCr), gamma-aminobutyric acid (GABA), glycerophosphocholine (GPC), phosphocholine (PCh), glucose, glutamine, glutathione, Glu, myo-inositol, lactate, Nacetylaspartate (NAA), N-acetylaspartate-glutamate (NAAG), scyllo-inositol and taurine as well as the combinations of Glu and glutamine (Glx), Cr and PCr (total creatine or TCr), of GPC and PCh (cholines or Cho), and macromolecules. After several iterations of data preprocessing, it fits the model basis set to the data and calculates the absolute concentration of each metabolite in mM taking the area under the corresponding fitted curve scaled to the water signal in the voxel. Processing of the multi-echo MRS data set allows precise measurement of Glu from the selective TE-averaged Glu signal, and can take into account T2 relaxation effects in the voxel. Water concentration in the voxel will be estimated by calculating the fractions of grey and white matter and cerebrospinal fluid in the voxel after segmentation of the T1-weighted structural MRI (Gasparovic et al., 2006; Kreis, Ernst, & Ross, 1993). [name] and/or his assistant will perform the MRS data processing. Glutamate level will then be compared between pre and post study drug administration. Changes in ACC glutamate level will be compared between the CLAV and placebo group using a one-sided Mann-Whitney-Wilcoxon Test at a significance level set to 0.05.

For all variables, first, preliminary and descriptive analyses will be conducted to assess data quality and integrity by descriptive statistical and graphical methods. Balances in terms of the demographic or disease characteristic variables between the groups will be empirically examined. Any systematic differences so identified will be noted in the study report of this proposal. Note that given the dramatically reduced new group sizes, all data analyses will be mostly descriptive and hypothesis generating in nature, and the results will be used primarily to guide the decision-making for the next step of this project.

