Using the intent-to-treat framework, the data will be reported using descriptive summary statistics such as mean, median, range, guartiles and standard deviation for a continuous variable and frequency and percentage for a categorical variable overall as well as by study group. Whenever appropriate, both point estimates and confidence intervals will be reported on the study endpoints of interest (e.g., changes in brain glutamate concentration and glutamate/creatine ratio). Differences for continuous variables will be assessed using t-tests (with unequal variances if appropriate) or the Wilcoxon rank sum test if the distributional assumption is violated for two-group comparisons. Proportions will be compared using the chi-square test or Fisher's exact tests. Multiple comparison adjustments will not be made due to the small sample size. Demographics and medical history variables (e.g., age, gender, and race) may be correlated to the study endpoints of interest, if strongly warranted. Some exploratory statistical approaches (e.g., Pearson/Spearman correlation coefficients, and linear regression for continuous variables) may be considered, if absolutely indicated by the study, to explore possible associations between the study endpoints and various covariates. We do recognize, however, due to small group sizes, such approaches

(correlation and regression analyses) may be not feasible to implement. Such analyses will not be employed unless absolutely warranted. To safeguard a possible departure from the normal distribution assumption, the appropriate nonparametric methods such as Wilcoxon rank sum test and Spearman correlation will be employed for analysis in addition to the usual parametric data analyses methods. SAS version 9.4 or higher will be used for all the data analyses.

Secondary Analyses

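### The primary glutamate comparison has a named test, but a general t-test-or-Wilcoxon rule under the same heading does not exempt it or say which p-value decides

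*Combined protocol and SAP*

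**What the plan says.** Three statements bear on the test for the primary endpoint. All stand in the Data Statistical Analysis Plan under Primary Analyses.

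1. After the description of the spectroscopy processing, changes in ACC glutamate are to be compared "between the CLAV and placebo group using a one-sided Mann-Whitney-Wilcoxon Test at a significance level set to 0.05".
2. The next paragraph widens the scope: "For all variables, first, preliminary and descriptive analyses will be conducted to assess data quality and integrity". The paragraph after that promises point estimates and confidence intervals for "the study endpoints of interest (e.g., changes in brain glutamate concentration and glutamate/creatine ratio"). The sentence that follows gives a general test rule: "Differences for continuous variables will be assessed using t-tests (with unequal variances if appropriate) or the Wilcoxon rank sum test", the latter "if the distributional assumption is violated for two-group comparisons".
3. Near the end of that paragraph, as a safeguard against non-normality, nonparametric methods "will be employed for analysis in addition to the usual parametric data analyses methods".

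The same paragraph adds: "Multiple comparison adjustments will not be made due to the small sample size".

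The Rationale for Sample Size section bases power on a one-sided Wilcoxon test with 3 and 9 subjects. Under Secondary Analyses, glutamine and craving are to be handled in the same way as glutamate, so whatever is unclear for glutamate carries over to them.

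**The concern.** Statement 1 gives one test, a direction and a level. Statement 2, read literally, covers every continuous two-group comparison and comes straight after a sentence that names the glutamate change. It would make the t-test the default. Statement 3 would run both. The general rule gives no direction, no criterion for a violated assumption or for when unequal variances are appropriate, and no order of precedence.

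An analyst who reported a t-test as the main glutamate result could claim to be following the plan. With three placebo subjects, the data can say very little about whether a distributional assumption holds, so the switch in statement 2 would rest largely on judgement made after the results are visible. The stake is whether a trial that will guide the next step of the programme is declared positive on a rule fixed in advance.

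**Working it through.** **Inputs.** From Rationale for Sample Size: 9 CLAV and 3 placebo subjects; group means 8.39 and 7.38, so a difference of 8.39 − 7.38 = 1.01; SD 0.76 in each group; alternative difference 1.68; stated power 63% and 94%; stated actual alpha 0.075 and 0.085. From Primary Analyses: one-sided Wilcoxon at 0.05. The simulations use normal data and 200,000 trials per setting.

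**Exact null distribution.** Let U be the number of the 3 × 9 = 27 CLAV–placebo pairs in which the CLAV change is the larger; a small U favours CLAV. There are C(12,3) = 220 equally likely arrangements.

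| Reject if | Exact one-sided alpha | Power at 1.01 | Power at 1.68 |
|---|---|---|---|
| U ≤ 3 | 7/220 = 0.0318 | 45.2% | 83.9% |
| U ≤ 4 | 11/220 = 0.0500 | 55.1% | 89.6% |
| U ≤ 5 | 16/220 = 0.0727 | 63.4% | 93.2% |

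**Reproducing the plan's figures.** Rejection at U ≤ 5 gives 63.4% and 93.2%, which match the stated 63% and 94%. The plan used 2000 Monte Carlo samples, so the standard error of its alpha is √(0.0727 × 0.9273 / 2000) = 0.006. The stated 0.075 fits 0.0727. The stated 0.085 is about two standard errors away, but 0.0727 is still the nearest attainable level. The stated power therefore belongs to a test at about 0.073, not at 0.05. At 0.05 the same test has 55.1% and 89.6%.

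**How often the candidate tests disagree.** All are one-sided at 0.05, with Wilcoxon rejecting at U ≤ 4.

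| | No effect | Difference 1.01 |
|---|---|---|
| Wilcoxon rejects | 4.9% | 55.1% |
| Pooled t rejects | 4.9% | 58.4% |
| Welch t rejects | 5.4% | 49.2% |
| Wilcoxon and pooled t differ | 2.2% | 9.9% |
| Wilcoxon and Welch differ | 3.2% | 16.3% |
| Wilcoxon or pooled t rejects | 6.0% | 61.7% |
| Any of the three rejects | 7.6% | 65.9% |

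**Illustration**, chosen because the tests differ. Placebo changes −0.3, −0.2, 0.7; CLAV changes −2.1, −1.9, −1.7, −1.6, −1.3, −1.2, −0.9, −0.1, 0.8. The CLAV value −0.1 exceeds two placebo values and 0.8 exceeds three, so U = 5. One-sided p-values: exact Wilcoxon 16/220 = 0.073, pooled t 0.035, Welch 0.018.

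**Unequal variances.** If the placebo SD is twice the CLAV SD (an assumption; the plan takes them as equal), the rejection rates with no effect are 12.2% for pooled t, 8.9% for Wilcoxon and 5.9% for Welch.

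**How the Wilcoxon p-value is obtained.** The plan does not say. At U = 4 the one-sided p is 0.0500 exactly, 0.048 by normal approximation with continuity correction (z = (4.5 − 13.5)/√29.25 = −1.66), and 0.062 by a t approximation with correction. U = 4 occurs in 55.1 − 45.2 = 9.9% of trials at the design effect. Reading the level as strictly below 0.05 would move the test to U ≤ 3.

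**The case against.** The strongest reply is that the primary test is already fixed. Only one sentence ties the glutamate comparison to a test, a direction and a level; the sample-size section uses the same test; and the secondary analyses refer back to glutamate as having its own described method. The general paragraph names glutamate in its sentence on estimates and intervals, not in its sentence on tests. By ordinary reading the specific rule prevails, and the later call for both kinds of test adds parametric results without replacing the Wilcoxon. The plan also says that, with groups this small, its analyses are largely descriptive and meant to generate hypotheses.

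Most of this stands. It makes the intent likely and lowers the severity. It does not close the gap, because the general rule contains no exemption and the plan keeps a formal test, a level and a power claim for this endpoint.

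A reader might go further and infer that the primary t-test could be two-sided, with a correspondingly larger disagreement. The documents do not support that: the general rule is silent on direction, and both places that specify the glutamate test say one-sided. A reader might also cite the 12.2% error of the pooled t-test under unequal variances as proof that Wilcoxon is safer. In the same setting Wilcoxon is itself inflated to 8.9%, and Welch is closest to nominal, so this is no argument for Wilcoxon over Welch.

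**Conclusion.** The concern holds as a gap in precedence. The plan most likely intends the one-sided Wilcoxon test to decide, but its general rule, under the same heading, leaves room for another test and names no deciding p-value. At the plan's own assumptions the choice would change the decision in about 10% of trials (pooled t) or 16% (Welch). With no effect the disagreement is 2% to 3%, and the type I error from taking the best result is 6.0% with two tests and 7.6% with three. These figures assume normal data, equal SDs, 12 completers and one-sided tests.

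It would be tempting to say that the plan has no prespecified primary test, or that the p-value method generally decides the result. Neither follows: a test is named, and the p-value method matters mainly when U = 4. The point should be fixed, but it is not critical in a 12-subject study whose stated purpose is mainly exploratory.

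**What to change.** Under Primary Analyses, state that:

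- the general test-selection rule does not apply to the primary comparison;
- the Day 10 minus baseline change in ACC glutamate is compared between CLAV and placebo by the one-sided Wilcoxon test alone, computed exactly and rejecting at exact p ≤ 0.05 (U ≤ 4, 11/220);
- t-test and Welch results for this endpoint are supportive and cannot change the conclusion.

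Say also whether the same applies to glutamine and craving, which follow the glutamate method.

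Restate Rationale for Sample Size to match: exact alpha 0.050, with power about 55% for a difference of 1.01 and about 90% for 1.68, in place of 63% and 94%. A shift estimate with a matching exact interval would be a useful addition but is optional.

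The cost is a few sentences and no further patients or data. The drawback is that the stated power becomes less favourable. The change should be made before treatment codes are opened.

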TREATMENT: The oral administration of CLAV 500,750,1000 mg/day or matched placebo for 10 days. Day 1 dosing is 1 capsule (250 mg) twice a day. Participants will receive 500mg CLAV in the morning on days 2 and 3 if the day 1 dose is safely tolerated. For those subjects who can tolerate 500 mg/day for 3 days (or matched placebo), there will be a forced dose escalation to 750 mg/day (or matched placebo) for 3 days. For those subjects who can tolerate 750mg/day (or matched placebo) for three days, there will be a forced dose escalation to 1000mg (or matched placebo) for 4 days. Participants who are unable to tolerate dose escalation will resume their previously tolerated dose. Nine subjects will be randomized to CLAV and 3 to placebo.

2) Protocol Title

A Phase IB Double Blind, Placebo Controlled, Pharmaco- Magnetic Resonance Spectroscopy (MRS) inpatient study of Clavulanic acid 500, 750,1000 mg daily repeated administration in early remitted cocaine use disorder subjects.

3) IRB Review History

Date:

03/27/2020 Initial submission to IRB (Modifications required)
04/17/2020 Modifications required to secure approval submitted (approved)
07/01/2020 Modification to include Covid Testing and Ace Questionnaire submitted (modifications required)

08/03/2020 Modifications required to secure approval submitted (approved) **09/17/2020** Modification to change dose self-administration procedures submitted (modifications required)

10/23/2020 Modifications required to secure approval submitted (approved) **11/02/2020** Modification to change screening and bonus schedule (modifications required)

11/03/2020 RNI (scanning schedule change) submitted

11/18/2020 Modifications for RNI submitted (approved)

11/30/2020 Response to modifications required for approval (approved)

12/01/2020: Modification to split screen into two parts and provide \$25 gift card compensation for Covid-19 testing (Modifications required)

12/23/2020: Response to modifications required to secure approval (approved)

03/29/2021: Temple Main Hospital and Jeanes added as back up inpatient sites (modifications required)

04/15/2021: Response to modifications required (approved)

05/13/2021: Eligibility Criteria Revised (approved)

4) Investigator

Primary Investigator/Medical Monitor:	[name]., M.S. (Temple University)
Co-Investigator/Imaging Specialist:	[name]. (Temple University)
Co-Investigator/Back up Medical Monito	or: M. [name]. (Temple University)

Other Key Personnel

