The primary outcome measures are changes in brain glutamate concentration in the anterior cingulate (ACC) after 10 days (steady state) of CLAV 500, 750, 1000 mg/day in subjects with cocaine use disorder compared with baseline. To normalize MRS data, an unsuppressed water signal acquired prior to or after the water-suppressed MRS scan in addition to the total creatine resonance will be used. The molecules present will be determined using the area under the curve corresponding to the concentration of the metabolite. [name], Harvard University, will supervise and perform the data analysis of the imaging data.

Secondary Outcome Measures

Secondary objectives are to:

A) To assess changes in craving-associated neurocircuitry (frontal-striatal-thalamic connectivity) using resting state functional Magnetic Resonance Imaging (rs-fMRI). Subjects with CocUD will have decreased functional connectivity between nodes within the frontal-striatal-thalamic network (Wang et al. 2018) involving mesocorticolimbic circuit nodes (Gu et al. 2010). After repeated CLAV, we expect that the fronto-striatalthalamic within network functional connectivity will increase. We also will determine whether improved network connectivity as associated with decreased craving as determined by the Cocaine Craving Questionnaire (CCQ) (Sussner et al. 2006) and a Visual Analog Scale (VAS). B) To evaluate whether CLAV 500, 750, 1000 mg a day given repeatedly for 10 days (to steady state, rationale below) and then stopped, is associated with a sustained reduction in brain glutamate concentration measured in the ACC one day after cessation of CLAV dosing (to determine the duration of CLAV action on glutamate after last dose and to determine the feasibility of once daily CLAV dosing). C) To evaluate whether 10 days of treatment with CLAV is associated with increases in brain glutamine concentration as assessed by MRS in the AC. D) To assess CLAV 500, 750, and 1000 mg/day safety and tolerability by: a) the rates of occurrence of adverse events; b) changes in vital signs; c) EKG parameters; and d) laboratory study changes.

Exploratory Outcome Measures

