Assessment of ACC Glu level one day after the last CLAV dose will be compared with the level on the last day of CLAV dosing. Resting state fMRI data preprocessing and analyses will be performed using statistical parametric mapping (SPM) (http://www.fil.ion.ucl.ac.uk/spm) based custom batch scripts (Wang et al. 2015, Wang et al. 2017, Li, Kadivar, et al. 2012, Li, Zhu, et al. 2012). Seed region-based functional connectivity (SRFC) will be calculated as the correlation coefficient (CC) of the resting state fMRI signal from a seed and any voxel in the rest of the brain. A Priori seeds will be defined in anterior cingulate (ACC), amygdala, ventral striatum (VS), insula, ventromedial prefrontal cortex (VMPFC), posterior cingulate cortex (PCC), and lateral prefrontal cortex (PFC). These regions are known to be affected by cocaine addiction, suggesting that their connections to other regions may be impaired as shown in (Gu et al. 2010) and may be predictive of relapse (Adinoff et al. 2015). ACC Regions of Interest (ROI) in the Montreal Neurological Institute (MNI) standard brain will be defined based on the previous SRFC work in cocaine addiction (Gu et al. 2010). Other seeds will be based on suprathreshold clusters from the literature or manually defined using the SPM Pickatlas utility (Maldjian et al. 2003). The individual subjects' FC maps will be first registered into the image space of the T1-weighted structural MRI and then registered into the MNI standard brain using SPM (version 12). The registration transform will be derived from the projection from the T1-weighted structural MRI to the MNI space.

There will be an assessment of glutamate level one day after the last dose compared with the last day of dosing after last dose.

Assessments for glutamine will be similar to those for glutamate.

Adverse events will be tabulated overall as well as by study group, and by body system and organ class if desired. In addition, all adverse events (AE's) noted during the study will be listed. The listings will include each occurrence of the AE, when it was reported, the severity and the duration. Adverse event data will be compiled for CLAV and placebo and presented as summary statistics. Subjective craving effects of CLAV from the visual analog scale and CCQ will be evaluated similarly as described in the above for glutamate.

Exploratory Analyses:

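### Adverse events are summarised by arm only, so the planned tables do not show at which dose level (500, 750 or 1000 mg/day) they arise, as objective D asks

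*Combined protocol and SAP*

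**What the plan says.** Under Statistical Plan, Secondary Outcome Measures, the fourth secondary objective reads "D) To assess CLAV 500, 750, and 1000 mg/day safety and tolerability by: a) the rates of occurrence of adverse events", followed by vital signs, EKG and laboratory changes. The abstract and section 5 state the same objective.

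Under Data Statistical Analysis Plan, Secondary Analyses, the planned displays are:

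- Tables: "Adverse events will be tabulated overall as well as by study group", with a split by body system and organ class left optional.
- Summary: "Adverse event data will be compiled for CLAV and placebo and presented as summary statistics".
- Listing: "In addition, all adverse events (AE's) noted during the study will be listed". Its content is then given: "The listings will include each occurrence of the AE, when it was reported, the severity and the duration".

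The general reporting paragraph of the Primary Analyses uses the same two groupings, overall and by arm, for all data.

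On dosing, the Study Drug Supply Description puts the escalation steps on Days 4 and 7. The treatment paragraph of the abstract adds: "Participants who are unable to tolerate dose escalation will resume their previously tolerated dose". Section 5 and section 20 (Dose Justification) say the same.

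**The concern.** The objective is framed by dose level and the summaries by arm. A single CLAV column mixes days at 500, 750 and 1000 mg/day.

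Dose level matters for safety in this study. Section 20 gives detection of adverse pharmacodynamic effects as a reason for including the two higher doses, and says that no maximum tolerated dose is established. In the background sections, the sponsor's own repeated-dose experience is a 10-day pilot at 500 mg, while the experience described at 750 and 1000 mg is with single doses. The Primary Analyses section says that the results are mainly to guide the next step of the project. A reader planning that step would want to know at which level events began and how many subjects were still at risk there.

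The sponsor has reported this way before: the background section breaks down adverse events in the earlier cocaine interaction study by dose day.

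**Working it through.** The documents give no rate, sample size or power for adverse events, so there is no stated figure to reproduce.

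**Does study day give dose?** For a subject who escalates fully, yes: Days 1–3, 4–6 and 7–10 correspond to 500, 750 and 1000 mg/day. For a subject who steps back, no: the same calendar day can be a day at a lower dose. These are the subjects with tolerability problems. The listing as described has no dose field, and the time of report is not necessarily the time of onset.

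**Exposure under full escalation.** Inputs are the allocation of 9 to CLAV and 3 to placebo (Randomization) and steps of 3, 3 and 4 days.

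- CLAV: 9 × 3 = 27, 9 × 3 = 27 and 9 × 4 = 36 subject-days; total 90.
- Placebo in the matching periods: 3 × 3 = 9, 3 × 3 = 9 and 3 × 4 = 12; total 30.

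**Per-day rate.** Assume (not in the documents) that the event rate is at background level on placebo and at 500 and 750 mg, and is r times background at 1000 mg. The pooled ratio is (3 + 3 + 4r)/10, so the share of the excess kept is 36/90 = 40%.

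| r at 1000 mg | Pooled ratio |
|---|---|
| 2 | 1.4 |
| 3 | 1.8 |
| 5 | 2.6 |

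If 3 of the 9 never stay on 1000 mg, the share kept falls to (6 × 4)/90 = 24/90, about 27%.

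**Proportion of subjects with any event.** Here the loss is smaller. The period risks are again assumptions.

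- CLAV 10%, 10% and 40%, against 10% per period on placebo. Over the course: 1 − 0.9² × 0.6 = 51% against 1 − 0.9³ = 27%. A 30-point difference at 1000 mg becomes 24 points.
- CLAV 20%, 20% and 50%, against 20% on placebo: 1 − 0.8² × 0.5 = 68% against 1 − 0.8³ = 49%. The 30 points become 19.
- If six CLAV subjects each have one event, all at 1000 mg, and all 9 reach that level, the proportion is 6/9 both at 1000 mg and over the whole course. There is no dilution.

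**What a table by dose could support.** With 0 events in 9 CLAV subjects at a level, the one-sided 95% upper limit is 1 − 0.05^(1/9) = 28%. With 0 in 3 on placebo it is 1 − 0.05^(1/3) = 63%. For a comparison of arms with 0/3 on placebo, at least 7/9 on CLAV are needed for Fisher's exact p < 0.05 (p = 0.045). Any such table is descriptive.

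**The case against.** The strongest reply is that the information is largely there. Every event is listed with its timing, adverse events are assessed daily, ingestion of each dose is observed, and Table 1 schedules an assessment for escalation on Days 3 and 6. With nine CLAV subjects, most events could be placed at a dose by hand. Serious and unexpected events also carry onset time, last dose and action taken with the drug (24-hour Reporting Requirements). The listing sentence need not be exhaustive. This stands. A reader might infer that the plan cannot answer objective D, and the documents do not support that: what is missing is a pre-specified display and a dose field.

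A reader might also infer that pooling dilutes any dose-related signal, and might point to 90/36 = 2.5-fold. That figure assumes that every event falls at 1000 mg and counts events per subject-day, whereas the general reporting paragraph plans frequencies and percentages. On percentages the loss is smaller and can be nil.

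The three doses may also be read as shorthand for the escalating regimen, since the matching endpoint refers to change from baseline without a dose split. That reading is possible, but section 20 gives the higher doses a safety purpose of their own.

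Finally, the protocol refers to an attached Data Safety and Monitoring Plan that is not among the documents. It may contain further displays.

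**Conclusion.** The point holds as a mismatch between objective D and the planned summaries. No summary by dose at onset or by escalation period is planned, the listing sentence names no dose, and the step-back rule means that study day does not always supply it. Many events could be assigned afterwards, but by a method not fixed in advance.

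The size depends on the measure. A pooled per-day rate keeps 40% of an excess confined to 1000 mg if all nine subjects escalate fully, and about 27% if three do not stay on that level. The proportion with any event loses less: 30 points become 24 or 19 in the examples, or nothing is lost. The excess and the period risks are assumptions.

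This is worth changing, but it does not touch the primary analysis. A table by dose would not isolate a dose effect either. Dose is tied to time in hospital and cumulative exposure, only those who tolerate a step reach the next, and three placebo subjects give little control for period.

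**What to change.** - Add onset date and actual dose at onset to the adverse event listing.
- Add one descriptive table of adverse events by actual dose level at onset (500, 750, 1000 mg/day, post-dosing). Show events, subjects with an event, subjects at risk and subject-days at risk, with placebo by matching study days. Count those actually exposed: dropouts are replaced, so more than 12 subjects may contribute at the lower levels.
- Report how many subjects completed or stepped back at each level.
- Summarise vital signs, and laboratory results at Days 3, 6 and 10, by actual dose in the same way. State that EKG cannot be split, because Table 1 schedules it only at screening and Day 10.
- State that the table is descriptive, for the reasons given in the verdict.

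The cost is some SAP wording and one extra table with small cells. The documents describe observed ingestion but no explicit daily dose record, so confirm that the case report form captures the dose actually taken each day. No dosing or clinical rule changes.
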